MM has two pre-cursor conditions: (i) monoclonal gammopathy of undetermined significance (MGUS) and (ii) smouldering multiple myeloma (SMM). MGUS and SMM reflect the early stages of MM, presenting with BMPC and Mprotein, but without end organ damage. MGUS is the earliest manifestation which is present in >4% of adults aged >50 years (Kyle et al., 2006; Dispenzieri et al., 2010) and, overall, carries a 1% risk of progression to MM per year (Kyle et al., 2002). MGUS can be broadly stratified into four risk cohorts, where progression risk in low-risk vs. high-risk cohorts is 5% and 58%, respectively at 20 years (Rajkumar et al., 2005). SMM reflects more severe disease and carries a 50% risk of progression at 5 years (Kyle et al., 2007). A 'watchful waiting' disease management approach is advocated for MGUS and SMM until symptoms of end organ damage arise (i.e. MM). This approach involves regular measurement of M-protein concentration with increasing frequency with more severe disease (e.g. for low-risk MGUS monitoring is only performed when MM symptoms arise; intermediate-high risk MGUS is typically monitored every 6 months for the first year, then annually; SMM is monitored every 2-3 months initially, decreasing to every 4-6 months and then 6-12 months if clinically stable (Korde, Kristinsson and Landgren, 2011)). The purpose of disease monitoring is to identify transformation to MM and commence active treatment, typically via chemotherapy and stem-cell transplantation (Ludwig et al., 2014). International guidelines do not currently recommend active treatment for MGUS or SMM (Kyle et al., 2010) due to the toxicity and cost consequences of anti-cancer drugs where the risk of disease progression is uncertain (Rajkumar et al., 2005), and uncertainty regarding the efficacy of therapy against all plasma cell clones (Campbell et al., 2017). However, risk stratification models highlight people with SMM and higher-risk MGUS as those who may benefit most from interventions to delay progression to symptomatic MM.

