Free-living measures

The participant will be given resources and equipment (i.e. an instruction pack), food diary, activity monitor and a sterile urine sample tube) for these measures at the screening visit after informed consent has been obtained. This allows measures to be completed prior to Visit 1 which will be scheduled a minimum of 9 days after screening.

Dietary composition: Participants will be provided with a 3-day food diary and instructions that explain how best to record everything they eat (e.g. portion size, cooking method, brand) for two weekdays and one weekend day. The records will be analysed using Nutritics software with the primary aim of characterising any changes to dietary intake between measurement points.

Physical activity: Participants will be given a BodyMedia Sensewear armband to wear for 9 days (to capture 7 full days) for measurement of free-living physical activity. The monitor is worn on the upper arm and records acceleration and skin temperature continuously. No identifiable data is collected by the BodyMedia Sensewear. Participants will be provided with instructions on how to use the monitor which emphasise the importance of wearing the monitor continuously aside from during waterborne activities e.g. showering/swimming. Data from complete days (>80% wear time) will be reported to examine any change in physical activity level between measurement points. The BodyMedia Sensewear will be loaned to the participant for the duration of measurement only. The devices are covered by the University of Bath insurance policy.

Urine sample: On the morning of Visit 1, participants will be asked to collect a mid-stream sample of their first-void urination in a universal, sterile sample tube for later analysis.

Visit 1

Participants will attend the University of Bath for a 1.5-hour measurement visit scheduled between 06:00 and 11:00 on a weekday. Participants will be asked to arrive fasted and having avoided caffeine since 22:00 the night before, and having avoided strenuous exercise and alcohol for 24 hours. A parking permit for the University will be given to participants at the screening visit. A sugary snack will be available for participants to consume following the visit.

Questionnaires

General health status: Incidence of recent infections, smoking status, alcohol intake (AUDIT-C), menopausal status (females only), stress (Perceived Stress Scale) and demographic information will be self-reported by the participant.

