Participants will complete a Session Record Card in each supervised session. Home-exercise will be monitored using a Home Exercise Diary which will be reviewed each week. Participants will also be provided with a fitness tracker (Polar A370 wrist-worn device) for the duration of the trial period to record all training sessions. Data from the tracker will be downloaded by the researcher once a week, and the tracker will be returned after Visit 4.

The primary outcome of feasibility refers to the overall viability of the exercise intervention (e.g. how well can we recruit, can we keep participants engaged, are participants able to achieve the exercise intensities required) and the safety (e.g. do adverse events occur and are they unexpected and related to the trial treatment):

Uptake: Proportion of people approached who attend screening (recruitment rate) and the proportion of people who attend screening that are deemed eligible (screen-pass rate). Demographic characteristics will be compared across those who a recruited and those who decline to participate.

Adherence: Number of supervised and home-exercise sessions completed measured using a Session Record Card, Home Exercise Diary and Polar A370.

Compliance: Prescribed vs. actual aerobic exercise completed in each supervised session will be measured using the Polar A370 and chest strap HR monitor. Compliance to home-based aerobic exercise will be measured using the Polar A370.

Retention: Proportion of participants who complete baselines measures (i.e. Visit 1 and 2) that also complete followup measures (i.e. Visit 3 and 4).

Safety: Incidence and severity of adverse events (Table 1). [Recording and reporting of SAEs will follow University of Bath policy – The chief investigator (CI) should report any SAE to the sponsor within 24 hours. A written SAE report (health research authority [HRA] form) should be made by the lead researcher and sent to the CI who will assess the seriousness, causality and expectedness. Where the SAE is related and unexpected, the CI will notify the research ethics committee (REC) within 15 days of receiving the report. AEs and SAEs will be discussed by the trial management group.]

Table 1. Definitions of a	Table 1. Definitions of adverse events						
Term	Definition						
Adverse Event (AE)	Any untoward medical occurrence in a participant to whom an intervention has been administered, including occurrences which are not necessarily caused by or related to that product.						

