Serious Adverse Event	A serious adverse event in the context of this trial is any untoward medical occurrence						
(SAE)	 that: results in death is life-threatening requires inpatient hospitalisation or prolongation of existing hospitalisation results in persistent or significant disability/incapacity Other 'important medical events' may also be considered serious if they jeopardise the participant or require an intervention to prevent one of the above consequences. 						

NOTE: The term "life-threatening" in the definition of "serious" refers to an event in which
the participant was at risk of death at the time of the event; it does not refer to an event
which hypothetically might have caused death if it were more severe.

Follow-up measurements

Free-living measurements will be repeated post trial-period (week 17). Resources and equipment (i.e. an instruction pack, food diary, activity monitor and a sterile urine sample tube) to complete these measures will be given to participants in their final exercise session.

After the trial period, participants will repeat baseline visits. Measurements conducted during Visit 3 will replicate Visit 1, and measurements conducted during Visit 4 will replicate Visit 2, as described above.

Participants will answer a physical activity questionnaire (IPAQ short-form) via telephone interview at time-points which coincide with routine disease monitoring during the 8 months following visit 4.

Withdrawal criteria

Participants may be withdrawn from the trial if there is a change in their eligibility e.g. disease progression to symptomatic multiple myeloma. During visit 2, contraindications and limitations to exercise may be identified during the CPET (Ats and Accp, 2003) which will result in participants being withdrawn on safety grounds. All withdrawals will be discussed with the haematologist and reported in primary outcomes (retention).

Storage of clinical samples

Samples will be collected and processed in a laboratory at the University of Bath:

- 15 mL into serum vacutainers, from which serum will be extracted and stored in multiple aliquots at -80°C for later analysis (e.g. disease activity, immune competence, inflammation, hormones and metabolic factors).
- 25 mL into a heparin-treated syringe, from which peripheral blood mononuclear cells (PBMCs) will be isolated by density gradient centrifugation and stored at −140 to −150°C for later analysis (e.g. phenotypic and functional measures of immune competence).

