Psychological sources of behaviour are important to consider when introducing a novel behaviour, i.e. an exercise programme, in order to optimise uptake, adherence, compliance and retention. Additionally, developing positive psychological processes in participants should increase the likelihood of continuing exercise after the trial ends for maintenance of any benefits attained. This reflects clinical practice in other exercise-based therapies delivered by the NHS (e.g. cardiac rehabilitation involves ~12 weeks of outpatient exercise classes [phase 3], after which patients transition to independent, ongoing conditioning in the community [phase 4]). In light of this, behaviour change techniques from a standardised taxonomy (Michie et al., 2011) have been included in the trial design (Table 4).

Table 4. Behaviour change con	siderations
Behaviour change technique	Implementation in present trial
Informational support	 Participants will be given detailed information about the exercise programme in the recruitment material, and will be encouraged to ask questions to ensure they understand the programme and the trial. At the end of the trial, the researcher will provide participants with information on local exercise referral schemes.
Information on consequences of behaviour	 The recruitment material describes the positive effects of exercise for health, explaining the rationale behind each component of the programme, which will be reinforced by the researcher during face-to-face interactions. Participants will be given a feedback report highlighting the health benefits attained during the exercise programme.
Feedback on performance	• Participants will be given regular feedback on how well they are meeting the progression targets set out in the exercise programme.
Self-monitoring	 Participants will be given a fitness tracker (Polar A370) to record habitual physical activity and home-based exercise, which will give feedback on their progress.
Instruction on how to perform behaviour	• The researcher will teach the participants how to perform the different exercises outlined in the exercise programme.
Social support	 Group exercise sessions will create a social environment for related peers, with the aim to keep classes at consistent times for each participant to allow relationships to be formed within the group. The researcher will facilitate grouped home-based exercises by identifying walking routes/meeting points for local participants.

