Substantial amendments to the documents submitted in the original REC application will be submitted using a valid notice of amendment to REC and to the trial sponsor. Non-substantial amendments will be made throughout the trial as needed. The CI will be responsible for determining whether an amendment is substantial. Substantial amendments will be highlighted in a new version of the document.

Data management and confidentiality

The University of Bath will act as the Data Controller for data generated by this trial.

Identifying data (name, date of birth, contact details and next of kin details) will be kept by the Royal United Hospitals Bath NHS Foundation Trust. This data will be stored in a password-protected Excel spreadsheet on a desktop computer stored in a locked room. This data will be deleted following the final study contact during the eight-month follow up. Signed consent forms will be stored in a locked cupboard and kept for 10 years to evidence the consent process.

Deidentified study data, coded with a unique study ID assigned to each participant, will be kept by the University of Bath. This data will be stored on the University of Bath X Drive which is backed up daily by the Library. The study-specific folder can only be accessed by the research team. Hard copies of trial data will be stored in a locked cupboard at the University of Bath. Study data will be kept for 10 years in line with the University of Bath research data policy (see: http://www.bath.ac.uk/research/data/policy/index.html).

Post-trial care

Participants will be given an information sheet upon completing the exercise programme with recommendations on staying active. This will include a home-exercise programme plus resistance bands, and information on local exercise referral schemes.

The researcher will telephone participants eight months following visit 4 – representing a full year since they entered the study. They will ask questions about current physical activity habits and identify participants who need additional information on how to lead an active lifestyle. Further signposting will be provided as a duty of care.

Access to the final trial dataset

All protocol contributors named in this document will have access to the final trial dataset. Requests for access by other researchers within the Department for Health at the University of Bath will be approved by the trial management group.

Dissemination policy

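### The 8-month physical activity follow-up has no guaranteed common time point: IPAQ calls follow routine monitoring, which varies with risk group, and the planned eight-month call does not name the IPAQ

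*Protocol*

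**What the plan says.** Aims and outcomes lists free-living physical activity and sedentary time as a secondary outcome, measured before and after the programme and again during an 8-month follow-up. Follow-up measurements says how the last part is collected: by IPAQ short form, "via telephone interview at time-points which coincide with routine disease monitoring during the 8 months following visit 4". No months and no number of calls are given, and the trial flow chart ends at week 17.

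Background and summary describes monitoring by risk group. At the low end there is no regular schedule: "for low-risk MGUS monitoring is only performed when MM symptoms arise". People with MGUS at higher risk are seen six-monthly in year one and yearly after that. The closest follow-up is for the more severe condition: "SMM is monitored every 2-3 months initially, decreasing to every 4-6 months and then 6-12 months if clinically stable".

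Post-trial care adds a separate contact: "The researcher will telephone participants eight months following visit 4". This call asks about current activity habits and offers signposting. It does not mention the IPAQ.

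On the tracker, Trial period measurements provides the Polar device for the trial period and says that "the tracker will be returned after Visit 4". Table 4 lists it as a self-monitoring technique, given "to record habitual physical activity and home-based exercise, which will give feedback on their progress". The armband measurement is made before Visit 1 and repeated in week 17. The Polar device is not mentioned at baseline.

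**The concern.** A maintenance estimate needs each participant measured at a comparable time. Here the timing and number of records are handed to the clinical monitoring schedule, which the protocol itself says depends on disease severity. People monitored more often would supply more records. People monitored rarely could supply one at an arbitrary month, or none. Any summary that pools the records, or takes whichever is available, would then mix differences in activity with differences in risk group and in time since the programme ended. The planned repeated-measures t-tests need one value per person at each time point, and this collection rule does not supply that.

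The eight-month call would solve the problem if it carried the IPAQ, but the two sections do not refer to each other. The pilot is meant to inform a later randomised trial, so it should give an interpretable figure for activity after the programme ends.

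The tracker raises a separate and smaller question. The week-17 armband measurement is labelled post-trial, yet one behaviour-change component is still in participants' hands, which was not so at baseline.

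**Working it through.** The protocol gives no figure for the number of follow-up records, so there is none to reproduce. The count below follows from its own description of monitoring.

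**Inputs.** Follow-up window W = 8 months (Follow-up measurements). Monitoring interval d, in months, from Background and summary. Assumption: local practice follows that description, which the protocol introduces as an example.

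**Count per person.** With regular visits every d months and an arbitrary starting phase, the mean number in the window is W/d, the minimum is W/d rounded down and the maximum is W/d rounded up.

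| Group | d | Mean = 8/d | Possible count |
|---|---|---|---|
| SMM, initial | 2-3 | 8/3 = 2.7 to 8/2 = 4.0 | 2 to 4 |
| SMM, later | 4-6 | 8/6 = 1.3 to 8/4 = 2.0 | 1 to 2 |
| SMM, clinically stable | 6-12 | 8/12 = 0.7 to 8/6 = 1.3 | 0 to 2 |
| Intermediate-high risk MGUS, first year | 6 | 8/6 = 1.3 | 1 to 2 |
| Intermediate-high risk MGUS, annual | 12 | 8/12 = 0.7 | 0 to 1 |
| Low-risk MGUS | none scheduled | not defined | set by symptoms |

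The count therefore runs from 0-1 (annual monitoring) to 4 (two-monthly monitoring). In a pooled set of records, a participant with 4 outweighs a participant with 1 by 4 to 1, that is 4/(4 + 1) = 80% of the pair's data.

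**Timing.** Taking each person's last record does not restore a common time. With interval d, the last visit falls up to d months before month 8. For d = 2 it lies between months 8 - 2 = 6 and 8. For d = 6 it lies between months 8 - 6 = 2 and 8. For d = 12 there may be none.

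**Does the eight-month call supply the common point?** Follow-up measurements names the instrument but no fixed time. Post-trial care names a fixed time but no instrument. Neither says that they are the same contact, so a common IPAQ record at eight months is possible but not guaranteed.

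**Does the same problem reach the pre-post comparison?** No. Baseline and week 17 use the same armband, worn for the same number of days. The IPAQ is given at Visit 1 and again at Visit 3, which replicates it. Each participant has one planned measurement at each point, whatever the risk group.

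**Tracker.** The tracker goes back after Visit 4, and the free-living measures are repeated in week 17, before the follow-up visits are complete. Participants therefore still possess it then. The text fixes possession. It does not require wear after training has ended.

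**The case against.** Several arguments weaken the point, and some of them stand.

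- The monitoring intervals are illustrative, and Recruitment draws on a database of people who are routinely monitored. This stands against a firm count of zero for low-risk MGUS: a reader might infer it from the background, but people with no routine monitoring may not be in the recruitment frame, and MGUS with no risk factors is enrolled last. The dependence on risk group remains for everyone else.
- Everyone is due a call at eight months, so a common contact exists. This stands as far as it goes. What is missing is the instrument and the link to the outcome.
- Timing the IPAQ with monitoring may be deliberate, because it pairs activity with a disease reading. The Visit 1 questionnaire section already plots past-year activity against disease activity. The follow-up section states no such purpose, but the pairing is worth keeping, so dropping the monitoring-linked calls would be the wrong remedy.
- The tracker is a declared part of the intervention, so an effect on activity is partly intended. This stands. The documents give no figure for reactivity to it, so an upward bias at week 17 is plausible but not quantified.

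A stronger reading is tempting: that the change in activity from baseline to week 17 is itself confounded with severity, or that the tracker is worn during the week-17 measurement. The documents support neither. The pre-post measures are taken at fixed points for all, and only possession of the tracker is stated.

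**Conclusion.** The point holds for the 8-month follow-up only. As written, the number and timing of IPAQ records depend on a monitoring schedule that varies with severity, from about 0-1 to 4 per person in 8 months, and no common time point is guaranteed. The range assumes that local practice resembles the protocol's background description. The lack of a fixed IPAQ time does not depend on that assumption.

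The tracker point holds in a narrow form: at week 17 participants have a self-monitoring aid available that is not mentioned at baseline, so the result cannot show activity without it.

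Severity is minor. Free-living activity is one of ten secondary outcome groups in a single-arm pilot of 20 (20 x 0.85 = 17 after the assumed 15% drop-out). The primary outcomes are untouched. The follow-up point is still worth correcting, because the analysis cannot easily repair uneven timing at this size and the correction is nearly free.

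**What to change.** 1. Reconcile Follow-up measurements with Post-trial care. State that every participant completes the IPAQ short form at the eight-month call, within a fixed window (for example plus or minus 2 weeks), and that this record is the maintenance estimate.
2. Keep any monitoring-linked IPAQ calls as additional descriptive data paired with the disease reading taken at the same time, outside the maintenance estimate.
3. For the tracker, choose one of three options: collect it after the last week-16 home session has been recorded and before armband wear begins; ask participants not to wear it in week 17; or report week 17 as activity with the tracker still available.

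**Cost.** The first two changes are wording plus a few more minutes on a call already planned. For the third, the tracker should not simply be taken back at the final supervised session: home-based compliance is a primary outcome measured with that device, and the last home session may come later. Collecting it after that session may need an extra contact. The other two options need only an instruction or a sentence in the report.

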In summary, the present pilot study aims to assess the feasibility and safety of an exercise programme in MGUS and SMM, and to provide preliminary data on disease activity, fitness and wellbeing outcomes for sample size calculations in a larger randomised controlled trial (RCT). Additionally, as part of this pilot study, a PhD project will investigate the potential mechanisms involved in possible changes in disease activity. Pilot data will allow a future larger randomised controlled trial to be designed optimally and to be adequately powered to assess the effect of exercise on disease activity, mechanisms and global fitness and wellbeing outcomes in MGUS and SMM. The unique clinical model proposed herein is anticipated to improve our wider understanding of how physical activity is linked to reduced cancer risk.

Aims and outcomes

The present trial will investigate the feasibility and safety of a 16-week progressive, walking-based exercise programme for MGUS and SMM.

Primary objectives and outcomes, measured throughout the trial period:

- Uptake (proportion of people approached who attend screening, proportion of people who attend screening that are deemed eligible)
- Adherence (proportion of supervised and home-based exercise sessions prescribed that are actually completed)
- Compliance (prescribed vs. actual aerobic exercise completed per supervised/home-based session)
- Retention (the proportion of participants who complete baselines measures that also complete follow-up measures)
- Safety (incidence and severity of adverse events)

Secondary objectives and outcomes, measured pre- and post-trial period:

- Disease activity of MGUS and SMM (M-protein, serum free light chains, beta-2 microglobulin)
- Physical fitness (VO_{2MAX}, balance, flexibility, strength)
- Free-living physical activity (e.g. duration, intensity, frequency, energy expenditure) and sedentary time (also measured during 8-month follow-up)
- Body composition (height, weight, waist and hip circumference, fat mass, lean mass, sagittal abdominal diameter)
- Wellbeing indices (frailty, fatigue, sleep, quality of life)
- CRAB indices (e.g. calcium; renal function [creatinine, estimated glomerular filtration rate; eGFR]; anaemia [full blood count, haemoglobin]; bone health [bone mineral density, bone mineral content, bone turnover biomarkers])
- Resting blood pressure and heart rate

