Quality of life: Health-related quality of life (QoL) will be assessed using the 36-item short form survey (SF-36) which includes eight domains: physical functioning; bodily pain; role limitations due to physical health problems; role limitations due to personal or emotional problems; emotional wellbeing; social functioning; energy/fatigue; general health perceptions and is validated for use with older adults. Overall QoL will be assessed using the Satisfaction with Life Scale: a 5-item questionnaire scored using a 7-point Likert scale that is validated for use in older adults.

Frailty: The International Myeloma Working Group (IMWG) frailty score is a validated questionnaire assessing aspects of frailty including comorbidities, basic activities of daily living (ADL) and instrumental ADL. The score is interpreted as fit (score = 0), intermediate-fitness (score = 1) or frail (score \geq 2). Increased frailty is associated with mortality and treatment toxicity in people with MM (Palumbo, Bringhen and Mateos, 2016). Reducing frailty prior to MM diagnosis (i.e. in people with MGUS and SMM) may delay a deterioration in frailty further along the disease continuum and therefore improve treatment outcomes and prognosis. The determinants of the frailty score are potentially responsive to exercise training, e.g. functional capacity and comorbid cardiovascular diseases.

Sleep quality: The Pittsburgh sleep quality index (PSQI) is validated to assess sleep quality and pattern in older adults. It is a 19-item questionnaire scored using a 0-3 Likert scale, with a total score >5 indicating poor sleep quality.

Fatigue: The functional assessment of chronic illness therapy (FACIT) fatigue scale is validated to assess fatigue in older adults. It is a 13-item scale scored using a 0-4 Likert scale, with a total score <30 indicating severe fatigue.

Physical activity: The international physical activity questionnaire (IPAQ) short-form is validated to assess moderate and vigorous intensity physical activity and sedentary time. Participants will be asked whether their responses are representative of the past year, e.g. whether their physical activity level has been stable or whether they can pin-point a distinct change (taking up a new exercise behaviour). This will be plotted against their past 1-year disease activity.

Resting measurements

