An important consideration for the research team when designing this study was the amount of time each participant will have to commit to the trial, which includes: 1 hour of screening and consenting, up to 5 hours of measurement visits and, finally, 32 exercise sessions (32 separate one hour visits). The screening visit has been planned to coincide with usual clinic hours at the haematology outpatients, so that people will be accustomed to the timing of this session, the familiarity of the physical environment and the practicalities of attending (e.g. parking, navigation of hospital). Trial measurement visits will be scheduled at a time of day according to the participant's availability. The exercise sessions will be run throughout the day and evenings to allow participants to choose the most suitable time for them to attend. These time considerations were made so that people who want to enrol, but are limited in terms of time availability can participate (e.g. if they have a job).

Statistics and data analysis

Sample size

The aim is to recruit 20 participants. Assuming a recruitment rate of three to four people per month and 15% drop out, we estimate the target can be reached within a suitable time-frame so the findings can be submitted for a PhD thesis (12-15 months).

There is limited information available to enable a formal sample size calculation. This pilot trial will provide preliminary data to determine that a future RCT has promise and is not futile, and to perform a sample size calculation.

Statistical analysis plan

Primary outcome measures do not lend themselves to statistical analysis. Feasibility will be reported as proportions in terms of uptake, adherence, compliance and retention. Safety will be reported as the incidence and severity of adverse events.

Secondary data will be tested for normality (e.g. Shapiro-Wilk) and in the event that some data are not normally distributed, the data will be log transformed. Descriptive statistics will be presented, and longitudinal differences and interaction effects will be identified using repeated-measures T-tests. These data will be used to inform sample size calculations in a future RCT. Incomplete data and missing values will be managed using an intention-to-treat approach with multiple imputation.

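### The plan identifies changes by a separate t-test on each of some 43 to 65 unranked secondary measures, so at a conventional 5% level most trials with no true change would still report at least one difference

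*Protocol*

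**What the plan says.** The protocol has its own Statistical analysis plan subsection under Statistics and data analysis. The primary outcomes (uptake, adherence, compliance, retention, adverse events) are to be reported descriptively. For the rest, it opens with "Secondary data will be tested for normality (e.g. Shapiro-Wilk", provides for log transformation where needed, promises descriptive statistics, and then states that "longitudinal differences and interaction effects will be identified using repeated-measures T-tests". Nothing limits that sentence to a subset of outcomes.

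Aims and outcomes lists the outcomes concerned under "Secondary objectives and outcomes, measured pre- and post-trial period". There are ten groups. The first is "Disease activity of MGUS and SMM (M-protein, serum free light chains, beta-2 microglobulin", which itself holds three markers. Others are broad, such as "Body composition (height, weight, waist and hip circumference, fat mass, lean mass, sagittal abdominal diameter" and "Wellbeing indices (frailty, fatigue, sleep, quality of life". Visit 1 widens the last of these, because the SF-36 is described as a survey "which includes eight domains: physical functioning; bodily pain" and six more. No group or measure is ranked above another, and no significance level or sidedness is stated.

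Under Sample size, the protocol says the pilot will "provide preliminary data to determine that a future RCT has promise and is not futile", and will support a sample size calculation.

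**The concern.** The wording makes the t-test the means by which a change is said to have occurred. Applied separately to several dozen measures with no lead measure, that rule will usually label something as changed even if the programme changes nothing. A reader of the results could not tell from the rule alone which labelled differences are chance. The pilot's secondary data are meant to inform a randomised trial, so what is at stake is how much weight those labelled differences receive when preliminary effect is described.

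**Working it through.** **No figure to reproduce.** The protocol gives no significance level, power, effect size or error rate, and says that information for a formal sample size calculation is limited.

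**Inputs**
- Recruited: 20, with 15% drop-out (Sample size). Completers: 20 × 0.85 = 17.
- Significance level: not stated. Assumed two-sided 5% per test, with 1% as a sensitivity check.
- Number of measures, lower count, taking only items named in Aims and outcomes: disease activity 3, fitness 4, free-living activity 5, body composition 7, wellbeing 4, CRAB 8, resting blood pressure and heart rate 2, immune 6, inflammation 1, metabolic 3. Sum = 43.
- Upper count, adding the scores described under Visits 1 and 2 and the markers named under Trial treatment (eight SF-36 domains, left and right grip and flexibility, two chair-stand scores, body mass index, body fat percentage, fat mass index, the activity questionnaire, named cytokine and growth-factor markers): 3 + 10 + 8 + 9 + 12 + 8 + 3 + 6 + 2 + 4 = 65.
- Working value: 50. The protocol states no total, and several lists are given only as examples.

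**Independent tests, no true change.** P(at least one) = 1 − (1 − α)^k, and the expected number of false differences is kα.

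| Measures k | α | P(at least one) | Expected false |
|---|---|---|---|
| 14 | 0.05 | 51.2% | 0.7 |
| 43 | 0.05 | 89.0% | 2.2 |
| 50 | 0.05 | 92.3% | 2.5 |
| 65 | 0.05 | 96.4% | 3.3 |
| 50 | 0.01 | 39.5% | 0.5 |

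**Correlated measures.** Paired t-tests were simulated with 17 pairs, no true change, 50 measures and α = 0.05. Correlation leaves the expected number at 50 × 0.05 = 2.5 but lowers the chance of at least one.

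| Correlation | Within the ten groups only | Common to all 50 measures |
|---|---|---|
| 0.3 | 90% | 82% |
| 0.5 | 86% | 63% |
| 0.7 | 79% | 43% |
| 0.9 | 66% | 21% |

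With 20 pairs the results agree within simulation error, so it makes little difference here whether 17 or 20 participants contribute. The chance falls below one half only if all measures share a common correlation somewhere above 0.5. That is hard to believe for changes in M-protein, sleep, flexibility and bone density taken together.

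**What one test can detect.** From the noncentral t distribution at two-sided 5%, power for a change of 0.5 SD is 49.1% at n = 17 and 56.5% at n = 20; for 0.8 SD it is 87.2% and 92.4%.

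**Why Bonferroni is not the answer.** At 0.05 / 50 = 0.001 per test the chance of any false difference is 1 − 0.999^50 = 4.9%, but power at 0.8 SD drops from 87% to 30% (n = 17) or from 92% to 42% (n = 20).

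**The case against.** The strongest reply is that a familywise error rate matters only where a familywise claim is made, and the protocol makes none. A reader might infer that any one p-value below 0.05 will be taken as showing promise, or that the randomised trial's outcome will be picked from whichever tests succeed, carrying an inflated effect into its sample size. The text supports neither inference. The statement about promise and futility sits under Sample size, refers to preliminary data in general, and could be met by the feasibility outcomes. The outcome areas for the randomised trial are already named in Background and summary. This part of the reply stands.

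It also stands that the secondary work is already called preliminary, that descriptive statistics are already promised, and that full multiplicity adjustment is not needed in an exploratory pilot. Nor would it be right to say that the tests cannot discriminate: each has a 5% false-positive rate against 49% power at 0.5 SD and 87% at 0.8 SD with 17 pairs. Weak power for moderate changes follows from the size of the pilot, not from this sentence. The calculation is also a null scenario, whereas some fitness gain after 16 weeks of supervised training is plausible.

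The reply that such detail may lie in a separate analysis plan goes only part of the way. A significance level or adjustment method could be set out there. But the protocol itself contains a section of that name and fixes there the rule by which differences are identified. The point concerns that stated rule.

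**Conclusion.** The point holds as a moderate one. Followed as written, the rule would attach the label of an identified difference to chance changes in most trials where nothing changed: about 66% to 92% for 50 measures as within-group correlation falls from 0.9 to zero.

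This rests on three assumptions: a two-sided 5% level (at 1% the independent figure is 39.5%, so the claim about most trials depends on the conventional level); a count of about 50 within a range of 43 to 65; and no strong correlation shared by all outcome groups. The consequence is a risk of over-reading chance findings. The documents do not show that a wrong decision about the randomised trial would follow.

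**What to change.** Replace the clause on t-tests with: *Each secondary outcome will be reported as mean (or geometric mean) change with SD of change and 95% CI; any p-values are exploratory and will not be used to declare differences.* Add that one disease-activity measure, chosen by the investigators and recorded before analysis (serum M-protein, listed first, is an example), is the lead measure for the statement on preliminary effect. A single lead measure tested at 5% would carry a 5% chance of a false finding.

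The change costs one or two sentences and uses the same data. It makes explicit the SD of change and the interval that a sample size calculation for the randomised trial needs. The downside is fewer results that can be called significant. False-discovery-rate control for any remaining p-values is optional and not part of the required change.
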